5.3. Determination of Sample Size

Approximately 960 patients will be randomized at a 1:1 ratio to ixekizumab and guselkumab. With 480 patients per treatment group, this study will have 98% power to test the superiority of ixekizumab to guselkumab for a 100% reduction in the Psoriasis Area and Severity Index (PASI 100) at Week 12. The following assumptions were used for the power calculation response rate at Week 12: 35.3% and 23.0% for the ixekizumab and guselkumab groups, respectively. A 2-sided Fisher's exact test at a significance level of 0.05 is assumed. This study is also powered at 95% to test the superiority of ixekizumab for PASI 100 at Week 24, assuming the response rate of ixekizumab and guselkumab at 56% and 44%, respectively. These assumptions are based on the ixekizumab and guselkumab clinical studies in psoriasis (Griffiths et al. 2015; Gordon et al. 2016; Blauvelt et al. 2017; Reich et al. 2017).

For the non-inferior test of PASI 100 at Week 24, a non-inferiority margin of -11.4% is considered sufficiently small to be clinically unimportant difference in outcome between guselkumab and ixekizumab. This non-inferior margin is based on a 70% retention rate approach assuming a placebo response rate of 6.0% at Week 24 observed in a phase 2 study (Deodhar et al. 2018). The sample size of 480 patient per treatment group provides >99% power to test the non-inferiority.

6. A Priori Statistical Methods

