6.1.3. Analysis Methods

The randomization to treatment groups is stratified by site, as described in Section 5.2. For statistical purposes, study sites with fewer than 5 randomized patients per treatment group will be pooled from smallest to largest (in terms of total number of patients per site and site identification number), until the pooled site had 5 or more patients per treatment group. If there are still sites with fewer than 5 patients per treatment group remaining after the pooling, those sites will be included in a pooled site with the smallest number of patients in total. Each pooled site will be considered as a single site for all efficacy and health outcome analyses.

The primary analysis method for treatment comparisons of categorical efficacy and health outcomes variables will be made using a Cochran-Mantel-Haenszel (CMH) test stratified by pooled site. Missing data will be imputed using the nonresponder imputation (NRI) method. The treatment response rates and their corresponding 95% confidence intervals (CIs), using normal approximation, as well as the treatment differences, will be reported. Secondary analysis will be conducted using a Fisher's exact test.

The primary analyses for the continuous efficacy and health outcome variables will be performed using mixed effects model for repeated measures (MMRM) analysis. The model will include treatment, pooled site, baseline value, visit, treatment-by-visit interaction, and baseline value-by-visit as fixed factors. A secondary analysis for continuous efficacy and health outcomes variables at specific time point will be made using analysis of covariance (ANCOVA) adjusting for pooled site and baseline value.

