summarized. Unplanned/Unscheduled measurements will be excluded from the MMRM analysis. However, the data will still be used in other analyses; such analyses include, but are not limited to, shift analyses and mBOCF endpoint analyses.

All CIs and statistical tests will be 2-sided with an alpha-level of 0.05, unless specified otherwise.

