Measure	Description	Variable	Derivation/Comment	Processing of Missing Components
		PGA-F (0, 1)	A PGA-F assessed as either 0 or 1, which represents a clinically meaningful response of clear or minimal nail psoriasis.	Missing if PGA-F is missing.
		PGA-F (0)	A PGA-F assessed as 0, which represents a clinically meaningful response of clear nail psoriasis.	Missing if PGA-F is missing.

Abbreviations: BSA = body surface area; eCRF = electronic case report form; EMA = European Medicines Agency; NPF = National Psoriasis Foundation; PASI = Psoriasis Area and Severity Index; PGA-F = Physician's Global Assessment of Fingernail Psoriasis; sPGA = Static Physician Global Assessment; VAS = visual analog scale.

Table RHCR 6.5. Description of Efficacy Outcomes Analyses

Measure	Variable	Analysis Method (Sections 6.1.3 and 6.3)	Analysis Population (Section 6.1.1)	Comparison/Time Point	Analysis Type
PASI	PASI 50	CMH test with NRI; Fisher’s Exact test with NRI	ITT Population; ITT population with PASI ≥ 12	IXE vs. GUS at Week 1 and all other postbaseline visits	Major secondary analysis is CMH test with NRI for ITT population comparing IXE vs. GUS at Week 1 (Section 6.11.2). Other analyses and comparisons are exploratory (Section 6.11.3).
	PASI 75	CMH test with NRI; Fisher’s Exact test with NRI	ITT Population; ITT population with PASI ≥ 12	IXE vs. GUS at Week 2 and all other postbaseline visits	Major secondary analysis CMH test with NRI for ITT population comparing IXE vs. GUS at Week 2 (Section 6.11.2). Other analyses and comparisons are exploratory (Section 6.11.3).
	PASI 90	CMH test with NRI; Fisher’s Exact test with NRI	ITT Population; ITT population with PASI ≥ 12	IXE vs. GUS at Weeks 4 and 8, and all other postbaseline visits	Major secondary analysis CMH test with NRI for ITT population comparing IXE vs. GUS at Weeks 4 and 8 (Section 6.11.2). Other analyses and comparisons are exploratory (Section 6.11.3).
	PASI 100	CMH test with NRI; Fisher’s Exact test with NRI	ITT Population; ITT population with PASI ≥ 12	IXE vs. GUS at Week 12, Weeks 4, 8, 24, and all other postbaseline visits	Primary analysis is CMH test with NRI for ITT population comparing IXE vs. GUS at Week 12 (Section 6.11.1). Major secondary analysis CMH test with NRI for ITT population comparing IXE vs. GUS at Weeks 4, 8, and 24 (Section 6.11.2). Other analyses and comparisons are exploratory (Section 6.11.3).

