6.17. Subgroup Analyses

6.17.1. Efficacy Subgroup Analyses

Subgroup analysis will be conducted on the following efficacy assessments:

- PASI 75, 90, 100 at Week 12 on ITT Population
- sPGA (0, 1) and sPGA (0) at Week 12 on ITT Population

A logistic regression model with treatment, subgroup, and the interaction of subgroup-by-treatment included as factors will be used. The subgroup-by-treatment interaction will be tested at the significance level of 0.10. Treatment group differences will be evaluated within each category of the subgroup using Fisher's exact test, regardless of whether the interaction is statistically significant. Missing data will be imputed using NRI. The treatment differences with 95% CIs by each subgroup category will be reported. If any group within the subgroup is <10% of the total ITT population, only summaries of the efficacy data will be provided (that is, no inferential testing).

The subgroups to be analyzed are listed in [Table RHCR.6.3](#). Additional subgroup analyses on efficacy may be performed as deemed appropriate and necessary.

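### Normal-approximation confidence intervals for single response rates would be too narrow at the first visits if few patients have yet responded (minor; free to improve)

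*SAP*

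**What the plan says.** The interval method for binary outcomes is set once, in SAP 6.1.3: the response rates in each arm and their 95% confidence intervals, "using normal approximation, as well as the treatment differences, will be reported". The normal approximation is attached to the response rates. No alternative is named for an arm with no responders or very few. The same section sets the level: "All CIs and statistical tests will be 2-sided with an alpha-level of 0.05, unless specified otherwise".

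Table RHCR 6.5 (SAP 6.11) fixes where the rule applies. For PASI 100 the comparison is "IXE vs. GUS at Week 12, Weeks 4, 8, 24, and all other postbaseline visits"; the PASI 90 row likewise covers Weeks 4 and 8 and every other postbaseline visit. The protocol's Schedule of Activities collects PASI at Weeks 1, 2 and 4, so these intervals are due from Week 1. PASI 100 at Week 4 is fourth in the testing sequence of SAP 6.4. PASI 90 and PASI 100 at Weeks 1 and 2 are labelled exploratory.

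The only PASI 100 rates assumed for the two arms are for Week 12 and Week 24 (SAP 5.3). For Week 12 they are "35.3% and 23.0% for the ixekizumab and guselkumab groups, respectively".

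**The concern.** The normal-approximation (Wald) interval estimates its own standard error from the observed proportion. When responders are very few, that estimate is too small, and it is exactly zero when there are none. The interval is then short, sits too low and can extend below zero. A report of 0 to 0 states certainty that 480 patients cannot give.

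The early visits are where this could occur. Complete or nearly complete clearance one or two weeks after the first dose is likely to be uncommon: the plan's own major secondary endpoints step up from PASI 50 at Week 1 to PASI 75 at Week 2 and PASI 90 and 100 at Week 4. Speed of onset is a stated purpose of the trial (protocol 3.1), so early response rates and their intervals are likely to be looked at. What is at stake is the accuracy of the label 95% on those descriptive intervals, not the outcome of any test.

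**Working it through.** **Inputs.** The sample size is 480 per arm (SAP 5.3: "With 480 patients per treatment group, this study will have 98% power to test the superiority of ixekizumab to guselkumab"), with patients "randomized at a 1:1 ratio to ixekizumab and guselkumab". Nonresponder imputation counts missing patients as failures, so the denominator stays at 480. Confidence level 95%, z = 1.96. Early true rates are an assumption, examined from 0.1% to 5%.

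**Reproducing the plan's own figure.** The documents state no interval width or coverage, so the check is on power. For 35.3% vs 23.0% with 480 per arm, the normal approximation gives 98.8% and full enumeration of the two-sided Fisher exact test gives 98.6%, against the stated 98%. The inputs are read correctly.

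**Formulas**, with p = x/n:
- Wald: p ± z√(p(1 − p)/n)
- Wilson: [p + z²/2n ± z√(p(1 − p)/n + z²/4n²)] / (1 + z²/n)
- Coverage at true rate π: the sum of binomial(n, π) probabilities over all x whose interval contains π
- Chance of a zero-width Wald interval from no responders: (1 − π)ⁿ

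**Intervals for small counts, n = 480 (%)**

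| Responders | Wald | Wilson |
|---|---|---|
| 0 | 0 to 0 | 0 to 0.79 |
| 1 | −0.20 to 0.62 | 0.04 to 1.17 |
| 2 | −0.16 to 0.99 | 0.11 to 1.51 |
| 3 | −0.08 to 1.33 | 0.21 to 1.82 |
| 5 | 0.13 to 1.95 | 0.45 to 2.42 |

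For 1/480, p = 0.208% and the Wald half-width is 1.96 × √(0.00208 × 0.99792/480) = 0.408%. For 0/480, the Wilson upper limit is z²/(n + z²) = 3.84/483.84 = 0.79%.

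**Exact coverage, n = 480**

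| True rate | Wald | Wilson | Chance of [0, 0] under Wald |
|---|---|---|---|
| 0.1% | 38.1% | 91.6% | 61.9% |
| 0.2% | 61.7% | 92.7% | 38% |
| 0.5% | 90.7% | 96.5% | 9.0% |
| 1% | 85.5% | 96.7% | 0.8% |
| 2% | 90.9% | 95.2% | 0.01% |
| 3% | 94.0% | 94.1% | negligible |
| 5% | 93.7% | 95.5% | negligible |
| 23.0% | 94.8% | 94.9% | negligible |
| 35.3% | 95.0% | 95.0% | negligible |

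Two rows in detail. At 0.1%, the chance of no responders is 0.999⁴⁸⁰ = 0.619, and each such result misses the true rate; that alone leaves at most 38.1%. At 1%, the Wald interval contains the true rate only for 3 to 11 responders. The chance of 0, 1 or 2 is 0.008 + 0.039 + 0.094 = 0.141, and the chance of 12 or more is about 0.004, so coverage is 1 − 0.145 = 85.5%. The shortfall therefore does not depend on a zero count. Coverage does not rise steadily with the rate because the count is discrete.

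**Subgroups (SAP 6.17.1).** These analyses are at Week 12 only, and inferential testing needs a group of at least 10% of the ITT population: 0.10 × 960 = 96 patients, about 48 per arm. At 48 per arm Wald coverage is 93.0% at 23.0% and 92.8% at 35.3%, with a negligible chance of no responders.

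**Differences between arms.** Wald coverage at 480 per arm is 94.9% for 35.3% vs 23.0%, 93.5% for 1% vs 0.2%, and 94.6% for 5% vs 1%. At 48 per arm with the planned Week 12 rates it is 94.4%.

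**The case against.** The strongest reply is that nothing in the documents puts an early rate near zero. The worst figures need true rates of 0.1% to 0.2%, which is an expected 0.48 to 0.96 responders among 480. At 1% the interval rarely collapses, and by 3% the shortfall has gone. Among the early endpoints in the testing sequence, PASI 50 at Week 1 and PASI 75 at Week 2 use lower thresholds; the most exposed results, PASI 90 and 100 at Weeks 1 and 2, are exploratory. Treatment claims rest on the stratified CMH test, with Fisher's exact test as the secondary analysis, and onset is also described by Kaplan-Meier and log-rank analyses of time to first response.

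All of this stands, and it makes the point minor and conditional. It does not remove it: the intervals are a promised output, the rule has no provision for sparse counts, and a valid test beside an interval does not correct that interval's coverage.

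A reader might go further and infer that intervals collapse in small subgroups, since SAP 6.17.1 promises that "The treatment differences with 95% CIs by each subgroup category will be reported". The documents do not support this. That sentence concerns differences and names no method, and the analyses are at Week 12, where the planned PASI 100 rates are far from zero and PASI 75 and 90 rates cannot be lower. Whether groups below 10% of the ITT population would still receive intervals is not stated. Nor does the coverage of Wald intervals for differences at the rates checked show that these must be replaced.

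**Conclusion.** The point holds, conditionally and as a minor one. The plan prescribes an interval that, at 480 per arm, covers 38% to 91% instead of 95% for true rates between 0.1% and 2%. It gives negative lower limits at 1 to 3 responders and no width at zero. Low rates at the first visits are plausible for PASI 90 and PASI 100, but they are an assumption, since no rate before Week 12 is given. From about 3% upward there is no material loss.

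A reader might infer that the trial's rapid-onset conclusions or its primary result are in doubt. They are not: the CMH and Fisher tests do not use these intervals, so the testing sequence and power are unchanged, and per-arm Week 12 intervals at the planned rates cover 94.8% and 95.0%.

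**What to change.** In SAP 6.1.3, replace the normal approximation with Wilson intervals for single response rates, at all visits. No change is needed to the tests, the testing sequence, the sample size or the intervals for differences.

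The cost is one phrase in the SAP and a standard option in SAS PROC FREQ. Nothing is lost where rates are moderate: at 23.0% coverage is 94.9% with Wilson and 94.8% with Wald, and at 35.3% it is 95.0% with both. At true rates of 0.1% to 2%, Wilson coverage is about 92% to 97%.

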6.2. Adjustments for Covariates

Randomization at the beginning of Period 2 is stratified by site. Unless otherwise specified, all efficacy and health outcome analyses during the Blinded Treatment Periods will include pooled site in the model.

In general, when an MMRM is used for analyses, treatment, pooled site, baseline value, visit, treatment-by-visit interaction, and baseline value-by-visit are included as covariates; when an ANCOVA is used for analyses, treatment, pooled site and baseline value will be included as covariates.

6.3. Handling of Dropouts or Missing Data

Intercurrent events (ICH E9 R1) are events which occur after the treatment initiation and make it impossible to measure a variable or influence how it would be interpreted. Potential intercurrent events include: missing scheduled visits, treatment discontinuation due to death or AEs, lost to follow-up, etc. The methods for handling missing data to be used in this study are in accordance with the precedent set in other Phase 3 psoriasis trials (Leonardi et al. 2008; Papp et al. 2008) and ixekizumab Phase 3 studies (RHAZ, RHBA, and RHBC).

6.3.1. Nonresponder Imputation (NRI)

An NRI imputation method can be justified based on the composite strategy (ICH E9 R1) for handling intercurrent events. In this strategy a patient is defined as a responder only if: (i) they meet the clinical requirements for response at the predefined time; and (ii) they remain on the assigned study treatment. Failing either criteria by definition makes them a nonresponder.

Binary efficacy and health outcome variables will be assessed using NRI. Patients will be considered nonresponders for the NRI analysis if they do not meet the clinical response criteria or have missing clinical response data at the analysis time point. Randomized patients without at least 1 postbaseline observation will also be defined as nonresponders for the NRI analysis.

6.3.2. Mixed-effects Model for Repeated Measures (MMRM)

An MMRM method can be justified based on the hypothetical strategy (ICH E9 R1) for handling intercurrent events. In this strategy, the effect of study treatment is assessed in a hypothetical trial where all patients have complete data and continue to take study treatment without dropping out of the study. The MMRM method assumes that missing data can bias results but the bias can be attenuated by modeling random effects using the within-subject error correlation structure. These correlations between the repeated measurements provide the platform used to account for the bias from subject dropout.

All continuous efficacy and health outcomes variables will be assessed using MMRM as a primary analysis. The MMRM model details are provided in Section 6.1.3.

6.3.3. Modified Baseline Observation Carried Forward (mBOCF)

An mBOCF imputation method can be justified based on the composite and while-on-treatment strategies (ICH E9 R1) for handling intercurrent events. The composite strategy handles an intercurrent event of a patient with treatment discontinuation due to AE by defining the patient as not receiving any benefit from study drug after the event. For the rest of intercurrent events, the effect of study treatment is assessed using the while-on-treatment strategy, based on the last observed value at or before the visit of interest, while the patient was still on study drug.

All continuous efficacy and health outcomes variables will be assessed using mBOCF as a secondary analysis. For a patient discontinuing study drug due to an AE, the baseline observation for the endpoint will be carried forward to the corresponding visit for all missing observations after the patient discontinued. For a patient discontinuing study drug for any other reasons, the last nonmissing postbaseline observation before discontinuation will be carried forward to the corresponding visit for all missing observations after the patient discontinued. For all sporadically missing observations prior to discontinuation, the last nonmissing observation before the sporadically missing observation will be carried forward to the corresponding visit. Randomized patients without at least 1 postbaseline observation will not be included for evaluation with the exception of patients discontinuing study drug due to an AE.

6.4. Multiple Comparisons/Multiplicity

A multiple testing strategy for the primary and major secondary objectives will be implemented to control the family-wise type I error rate at a 2-sided alpha level of 0.05. The primary and major secondary endpoints will be sequentially tested in the following order to compare ixekizumab (IXE) versus guselkumab (GUS), using the primary analysis method.

- 1) Proportion of patients achieving PASI 100 at Week 12 (NRI) – IXE versus GUS
- 2) Proportion of patients achieving PASI 75 at Week 2 (NRI) – IXE versus GUS
- 3) Proportion of patients achieving PASI 90 at Week 4 (NRI) – IXE versus GUS
- 4) Proportion of patients achieving PASI 100 at Week 4 (NRI) – IXE versus GUS
- 5) Proportion of patients achieving PASI 90 at Week 8 (NRI) – IXE versus GUS
- 6) Proportion of patients achieving sPGA (0) at Week 12 (NRI) – IXE versus GUS
- 7) Proportion of patients achieving PASI 50 at Week 1 (NRI) – IXE versus GUS
- 8) Proportion of patients achieving PASI 100 at Week 8 (NRI) – IXE versus GUS
- 9) Proportion of patients achieving PASI 100 at Week 24 (NRI) – IXE versus GUS

If a test in this sequence is not significant, all subsequent tests will be considered nonsignificant.

There will be no adjustment for multiple comparisons for any other analyses.

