In 2 recent Phase 3 studies, VOYAGE 1 (Blauvelt et al. 2017) and VOYAGE 2 (Reich et al. 2017), guselkumab treatment (administered as a single 100-mg injection initially, 4 weeks later and subsequently every 8 weeks [Q8W]) resulted in statistically significant improvements in efficacy compared with placebo and superiority to adalimumab, a TNFi, in the treatment of moderate-to-severe Ps (Gordon et al. 2018). In the VOYAGE 1 study, compared with placebo, significantly higher proportions of patients taking guselkumab achieved Investigator Global Assessment (IGA; co-primary endpoint) 0/1 (6.9% vs. 85.1%) and PASI 90 (co-primary

endpoint; 2.9% vs. 73.3%) at Week 16. In addition, the proportions achieving IGA 0 (1.1% vs. 47.7%) and PASI 100 (0.6% vs. 37.4%) were significantly higher for guselkumab vs. placebo at Week 16. Compared with adalimumab, a higher proportion of patients in the guselkumab group achieved IGA 0/1 (85.1% vs. 65.9%) and PASI 90 (73.3% vs. 49.7%) at Week 16. Significantly better responses to guselkumab compared with adalimumab were maintained at Week 24 and at Week 48; PASI 100 responses in the guselkumab group were also significantly better than those in the adalimumab group at Weeks 24 and 48. The results of VOYAGE 2 study confirmed the results of VOYAGE 1. Guselkumab was superior to placebo at the Week 16 co-primary endpoints (IGA 0/1 and PASI 90). Guselkumab was also superior to adalimumab at the Week 16 endpoints (IGA 0/1, PASI 75/90) and at Week 24 (IGA 0, PASI 90, and PASI 100).

Adalimumab is one of the earliest biologics approved for Ps and targets the TNF pathway. Guselkumab, being one of the most recent biologics, targets the IL-23 pathway. As the IL-17/23 pathway has been shown to be selectively important in the pathogenesis of Ps (Leonardi et al. 2012; Langley et al. 2014; Sofen et al. 2014; Gordon et al. 2015; Griffiths et al. 2015; Krueger et al. 2015; Lebwohl et al. 2015; Papp et al. 2015), the results of the VOYAGE studies (guselkumab [IL-23p19 antagonist]) are not surprising, nor are the results of the UNCOVER-2 and -3 studies that demonstrated superior efficacy of ixekizumab (IL-17A antagonist) compared to the TNFi etanercept. These studies help inform dermatologists that newer biologics have superior efficacy compared to older biologics targeting the TNF pathway and, thus, are a good choice for treating patients who desire nearly clear or completely clear skin.

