### **10.3.7. Interim Analyses**

One interim analysis is planned when all patients have completed their Week 12 visit or ETV. The interim analysis will include all data collected by the cutoff date, including the data from the Extension Period (Period 3) and the Post Treatment Follow-Up Period (Period 4). The analyses from the Week 12 lock will be treated as a primary analysis because all primary and major secondary objectives, except for PASI 100 at Week 24, will be assessed at this time.

Prior to a Week 12 database lock, all members of the study team will be blinded to the treatment allocations. At the time of the Week 12 database lock, study team members that do not have direct access to study sites will have access to the unblinded treatment allocation and unblinded data. Study team members that have direct access to study sites and data collection will remain blinded to the treatment allocations until all patients have completed the study (or discontinued on or prior to Week 24) and final database lock has occurred. Site staff, clinical monitors, and patients will remain blinded to the patient treatment allocation until after final database lock.

Information that may unblind the study during the analyses will not be reported to study sites or blinded study team until the study has been unblinded. All investigators, patients and personnel in contact with study sites will be kept blinded to treatment assignments until final CSR is complete.

Additional analyses and snapshots of study data may be performed after all patients complete Period 3 (Week 24 or ETV) to fulfill the need for regulatory interactions or publication purposes.

Unblinding details are specified in the unblinding plan section of the SAP or a separate unblinding plan document.

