
Exploratory To assess whether ixekizumab is superior to guselkumab in the treatment of patients with moderate-to-severe plaque psoriasis at different time points, as measured by:
 
 • sPGA (0, 1) • Itch NRS • Skin Pain VAS • DLQI (0,1) 
To assess whether ixekizumab is non-inferior
	
 • The proportion of patients with a static sPGA (0,1) at Weeks 4, 8, 12, 24 • The proportion of patients achieving the Itch NRS Responder definition at Weeks 4, 8, 12, and 24 (restricted to those patients with Itch NRS score ≥ 4 at baseline) • Change from baseline in Itch NRS score at Weeks 4, 8, 12, and 24 • The proportion of patients achieving Itch NRS (0) at Weeks 4, 8, 12, and 24 (restricted to those patients with Itch NRS score >0 at baseline). • The proportion of patients achieving Skin Pain VAS (0) at Weeks 4, 8, 12, and 24 (restricted to those patients with Skin Pain VAS >0 at baseline) • Change from baseline in Skin Pain VAS score at Weeks 4, 8, 12, and 24 • The proportion of patients achieving DLQI (0,1) at Weeks 2, 4, 8, 12, and 24

Objectives	Endpoints
to guselkumab in the treatment of patients with moderate-to-severe plaque psoriasis at Week 24, as measured by: 
 • PASI 100 	
 • Proportion of patients achieving PASI 100 at Week 24

Abbreviations: DLQI = Dermatology Life Quality Index; NRS = Numeric Rating Scale; PASI = Psoriasis Area and Severity Index score; sPGA = static Physician Global Assessment; VAS = visual analog scale.

5. Study Design

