6.11.3. Exploratory Efficacy Analyses

The exploratory efficacy analyses will be based on the ITT population except:

- Physician's global assessment of disease activity visual analog scale (VAS): based on the ITT population – patients with baseline psoriatic arthritis
- PGA-F: based on the ITT population – patients with baseline PGA-F ≥ 3

These analyses will be conducted on the Blinded Treatment Periods. There will be no adjustment for multiple comparisons. The exploratory efficacy analyses are detailed in Table RHCR 6.4 and Table RHCR 6.5.

The following additional summaries will be provided for each treatment group:

- Among PASI 50 responders at Week 1, proportion of patients achieving PASI 75, PASI 90, and PASI 100 at Week 12, respectively.
- Based on the ITT population with PASI ≥ 12 at baseline, proportion of patients achieving PASI 50, PASI 75, PASI 90, and PASI 100 at each post-baseline visit, respectively.
- Based on the ITT population with sPGA ≥ 3 at baseline, proportion of patients achieving sPGA (0) and sPGA (0, 1) at each post-baseline visit, respectively.

For assessing the non-inferiority of ixekizumab to guselkumab in PASI100 at Week 24, missing PASI data at Week 24 will be imputed using NRI method outlined in Section 6.3.1.

Non-inferiority analysis will be performed on the ITT population using a pre-specified fixed margin approach, with the non-inferiority margin of -11.4%. The non-inferiority will be established if the lower bound of the 2-sided 95% CI for the difference in proportion of responders on the ixekizumab minus guselkumab is greater than the pre-specified margin. The CI for the difference in proportion will be calculated using the simple asymptotic method without continuity correction.

Area under the curve (AUC) for PASI 75, PASI 90, PASI 100, sPGA (0,1), itch NRS \geq 4 point improvement for patients with baseline itch NRS \geq 4, itch NRS (0), and DLQI (0,1) at weeks 12, 16, and 24 will be analyzed and compared between ixekizumab and guselkumab. AUC for each individual patient data (IPD AUC) based on the exact date of each visit and the responder status or improvement value for that patient will be calculated; total IPD AUC will be determined as the sum of the AUC over all visits during the study period. Treatment differences in terms of AUC will be compared using an analysis of covariance (ANCOVA) model after adjusting for baseline PASI values.

The AUC analyses will be conducted after the final database lock.

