6.18. Interim Analyses

The study will have one interim database lock once all patients complete Visit 9 (Week 12) or discontinue in the Induction Dosing Period. The interim analysis will include all data collected by the cutoff date, including the data from the Extension Period and the Post Treatment Follow-Up Period. The interim database lock at Week 12 will be considered the primary database lock because all primary and major secondary objectives, except for PASI 100 at Week 24, will be assessed at this time.

Prior to the Week 12 database lock, all members of the study team will be blinded to the treatment allocations. At the time of the Week 12 database lock, study team members that have direct access to study sites and data collection will remain blinded to the treatment allocations until all patients have completed the study (or discontinued on or prior to Week 24) and final database lock has occurred. Site staff, clinical monitors, and patients will remain blinded to the patient treatment allocation until the final Clinical Study Report (CSR) has been approved.

A final database lock will occur after the Post-Treatment Follow-Up Period is completed.

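### Week 24 PASI 100 non-inferiority is specified like a confirmatory test but left exploratory; making it the step before Week 24 superiority would protect it at almost no cost

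*SAP*

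**What the plan says.** SAP Section 5.3 sets a fixed margin of -11.4% for PASI 100 at Week 24, based on 70% retention with a 6.0% placebo rate, and adds: "The sample size of 480 patient per treatment group provides >99% power to test the non-inferiority". The same section powers Week 24 superiority at 95%, assuming 56% on ixekizumab and 44% on guselkumab.

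SAP Section 6.11.3 supplies the decision rule on the ITT population with NRI: "The non-inferiority will be established if the lower bound of the 2-sided 95% CI" for the difference lies above the margin. The interval is the simple asymptotic one, without continuity correction.

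The status is different. In SAP Table RHCR.4.1 the objective ("To assess whether ixekizumab is non-inferior") stands under the exploratory heading. The fixed sequence in SAP Section 6.4 has nine tests and ends with Week 24 PASI 100, which is the superiority objective. For everything else, "There will be no adjustment for multiple comparisons for any other analyses". The protocol has no non-inferiority objective in its synopsis, Table RHCR.4.1 or Table RHCR.10.1.

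**The concern.** The test has the parts of a confirmatory claim (margin, power, a rule for when it is established) but exploratory standing. Week 24 PASI 100 is the only primary or major secondary endpoint after Week 12. If superiority is missed there, the trial has no confirmatory Week 24 conclusion, even when the interval clearly excludes the margin. As written, non-inferiority could also be called established after the sequence has stopped at an earlier step.

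Timing matters. At the Week 12 lock, "The interim analysis will include all data collected by the cutoff date, including the data from the Extension Period" (SAP Section 6.18), and under Protocol Section 10.3.7 "study team members that do not have direct access to study sites will have access to the unblinded treatment allocation and unblinded data". Promoting the test after that point could look data-driven.

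**Working it through.** **Inputs.** 480 per arm; Week 24 rates 56% and 44%; margin -11.4 points; placebo rate 6.0%; 70% retention (all SAP 5.3). Wald 95% interval (SAP 6.11.3). CMH test stratified by pooled site for superiority (SAP 6.11.2). Dropouts count as nonresponders, so 480 is not reduced.

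**1. The plan's own figures reproduce.**
- Margin: (1 - 0.70) × (44 - 6.0) = 11.4 points.
- Week 24 superiority, pooled-variance z: (0.12 - 1.96 × √(2 × 0.25/480)) / √(2 × 0.56 × 0.44/480) = 1.77, so power is 96.2%. Exact Fisher gives 95.5%. Stated: 95%.
- Non-inferiority at 56% vs 44%: (0.12 + 0.114)/0.0320 - 1.96 = 5.34, so power exceeds 99.9%. Stated: >99%. This rests on the assumed 12-point advantage; at equal 44% rates it is 94.4%.

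**2. How often is superiority missed but non-inferiority met?** Exact enumeration of all 481 × 481 = 231,361 outcome tables. Superiority is pooled z > 1.96, the unstratified analogue of CMH. Non-inferiority is Wald lower bound > -0.114.

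| Ixekizumab vs guselkumab | Superiority met | Non-inferiority met, superiority missed |
|---|---|---|
| 56% vs 44% | 96.1% | 3.9% |
| 54% vs 44% | 87.2% | 12.8% |
| 52.2% vs 44% | 71.7% | 28.3% |
| 50% vs 44% | 45.6% | 54.3% |
| 44% vs 44% | 2.4% | 92.0% |

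The gap drives the result, not which arm moves: an 8-point gap gives 30.0% to 30.4% at 48 vs 40, 50 vs 42, 54 vs 46 and 56 vs 48. Only the first row is a planning assumption. The 52.2% is a Week 52 rate from another ixekizumab trial (Protocol 3.2), used as a sensitivity value. In every row non-inferiority is true.

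**3. What error control exists now?** Consider false claims in favour of ixekizumab.
- True difference at or below -11.4 points: superiority outcomes are a subset of non-inferiority outcomes, so the chance of any false claim in the pair is that of the non-inferiority rule, 2.5% at 32.6% vs 44%.
- Between -11.4 and 0: only superiority can be claimed falsely.
- Above 0: neither can.

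Over guselkumab rates of 40%, 44% and 50% and differences from -20 to +12 points, the pair's error never exceeds 2.6% one-sided. Inflation needs two things together: an earlier null hypothesis is true, so that the sequence rightly stops, and ixekizumab is truly at least 11.4 points worse at Week 24. The chance of at least one false claim is then at most 2.5% + 2.5% = 5.0% one-sided (1 - 0.975² = 4.9% if independent, 4.5% at an assumed correlation of 0.5).

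**4. What does the added step cost superiority?**
- Pooled z: 104,221 tables show superiority and 0 of them fail non-inferiority. Fisher: 0 of 103,757. The smallest lower bounds are about +0.01 and +0.2 points, against -11.4.
- Stratified CMH against the unstratified Wald rule, simulated under assumed site structures. In 4,000,000 trials (60 sites of 8 per arm or 96 of 5 per arm; site log-odds SD 0 or 0.7), 0 had superiority without non-inferiority. In a second set (24, 48 or 80 sites; SD 0 or 0.8; 20,000 trials per setting) there were again 0, with a lowest bound of about -0.7 points, so 11.4 - 0.7 = 10.7 points clear.

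**The case against.** The strongest reply is that the plan is consistent. Section 6.4 limits family-wise control to the primary and major secondary objectives, non-inferiority is openly exploratory, and an exploratory analysis may have a prespecified margin and rule. That stands: promoting the test is a choice of objectives, not the repair of a contradiction.

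A reader might infer that the SAP lets error run uncontrolled whenever superiority is missed and non-inferiority met. The documents do not support this. When tests 1 to 8 succeed, the Week 24 pair is already held at about 2.5% one-sided, and inflation requires a truth far from the planned 12-point advantage. Nor are the percentages in the table error rates.

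It is also fair that the fix is not free. A miss on, say, PASI 50 at Week 1 (test 7) would block the confirmatory claim. The documents give no rates for tests 2 to 8, so the gain cannot be fully quantified, and the table overstates it to that extent. Non-inferiority could still be reported as exploratory after such a miss, which is its status today.

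Finally, the placebo rate behind the margin comes from a phase 2 study in psoriatic arthritis (SAP references). That does not make the margin lenient. Protocol 3.2 reports "PASI 100 (0.6% vs. 37.4%) were significantly higher for guselkumab vs. placebo at Week 16"; with 0.6% the same formula gives 0.3 × (44 - 0.6) = 13.0 points, so -11.4 is the stricter value.

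**Conclusion.** The point holds as a cheap improvement. The plan forgoes a confirmatory Week 24 conclusion that it has already specified. The loss is small if the 12-point assumption is right and large if the true gap is about half that. It should not be read as a breach of the stated family-wise control, nor as a fault in the 95% superiority power or in the margin.

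The result rests on 480 per arm and on the pooled-variance test as a stand-in for CMH. Nesting of superiority within non-inferiority is exact for the unstratified tests. For stratified CMH against an unstratified interval it holds by more than 10 points under assumed site numbers and heterogeneity, not by identity.

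**What to change.** Before the Week 12 unblinding:
- In SAP 6.4, make step 9 Week 24 PASI 100 non-inferiority (ITT, NRI, margin -11.4%, 95% interval as in 6.11.3) and step 10 Week 24 PASI 100 superiority.
- Move the objective to major secondary in SAP Table RHCR.4.1, move the analysis from 6.11.3 to 6.11.2, and update SAP Table RHCR 6.5.
- Add it to the protocol synopsis, Table RHCR.4.1 and Table RHCR.10.1.
- State that, if an earlier test fails, non-inferiority is reported descriptively as exploratory and not as established.

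The cost is a small SAP amendment, a small protocol amendment because a major secondary objective is added, and the dependence of the confirmatory claim on tests 1 to 8. No patients, visits or data are added, and the margin is unchanged.
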